5.2.2 Secondary safety endpoints

Safety endpoint of all major adverse cardiac events (MACE) defined as all- cause death or survived sudden cardiac arrest, myocardial infarction, re-hospitalisation for acute coronary syndrome, acute unplanned PCI, coronary artery bypass grafting (CABG) and documented life-threatening arrhythmias (VF, VT, AV-block III)at 30 days.

MACE at 90 days

All-cause death at 30 days

Re-hospitalisation for suspected acute coronary syndrome at 30 days

Acute Myocardial Infarction (AMI)

Acute unplanned PCI

CABG

Documented life-threatening arrhythmias or survived sudden cardiac arrest

Rate of bleeding events defined as non-CABG intracranial, intraocular, or retroperitoneal bleeding; access-site hemorrhage requiring intervention or resulting in a ≥ 5 cm diameter hematoma; reduction in hemoglobin concentration of ≥ 4 g/dL without or ≥ 3 g/dL with an overt bleeding source; reoperation for bleeding; or blood product transfusion.

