5.1 Primary endpoint

Rate of MACE (all- cause death or survived sudden cardiac arrest, myocardial infarction, re-hospitalisation for acute coronary syndrome, acute unplanned PCI, coronary artery bypass grafting (CABG) and documented life-threatening arrhythmias (VF, VT, AV-block III)) within 30 days Copeptin vs. Control group

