7.1 General Patient Flow

Consecutive N-STEACS patients of the Chest Pain Unit with a negative Troponin T at admission will be invited to participate. Troponin T is tested as part of the standard management of patients with suspected acute coronary syndrome. Patients who give their written informed consent will be randomized into one of two study arms (experimental and standard management).

Experimental Arm: Further management dependent on Copeptin result

1. Patients of the above described characteristics who test **negative for Copeptin** at admission will be considered low-risk. In these patients we abstain from further ACS evaluation and instead discharge them into ambulant care. Before discharge patients will have a final visit to secure their well-being. The visit includes a physical examination, an ECG and an assessment for MACE and bleeding events.

Patients who show any signs and symptoms of an acute illness requiring in-hospital treatment will not be discharged (see withdrawal criteria 5.3). This decision is at the discretion of the attending physician.

To secure the patients safety they will be discharged into each co-operating network of resident cardiologists . Patients are to see a cardiologist within a maximum of 3 days after discharge (if discharge falls on a Friday), preferably on the next day after discharge. Further appointments will be at the discretion of the resident cardiologist (see 7.2).

2. Patients with the above described characteristics who test **positive for Copeptin** at admission will be managed as by standard practice i.e. patients will be evaluated as by standard of care abiding current guidelines for the management of patients with suspected ACS

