8.6 Clinical processes

Procedure	Screening	Enrolment	Randomization	Discharge	30d	90d
Screening Log	x					
Medical history	x					
Physical exam.	x					
Routine -ECG	x					
Blood routine*	x					
Copeptin		x**				
Informed consent		x				
Copeptin result request			(x) ***			
Questionnaire contentedness				x		
MACE and bleeding event assessment				x	x	x

- Including Troponin and CK

**request from routine blood sample from screening period

*** only for patients in experimental group

All in-hospital examinations are standard practice of care in patients with suspected ACS. The deviations concern the process of patient management – early discharge of Copeptin negative patients and further evaluation of high-risk ACS of Copeptin positive patients - rather than in-hospital examinations. All CPU patients are under constant monitoring and risk assessment.

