8.7 Follow-up

All patients will have a 30-day and a 90-day follow-up. Both follow-ups are telephone visits to assess:

- Survival
- MACE and bleeding complications

In case of death or hospitalization during the study period medical records will be requested. The patient will consent to this in the informed consent form.

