11.1 Definition

Major adverse cardiac event (MACE) is defined as

- All- cause death or survived sudden cardiac arrest
- myocardial infarction
- Re-hospitalisation for acute coronary syndrome
- Acute unplanned PCI
- Coronary artery bypass grafting (CABG)
- Documented life-threatening arrhythmias (VF, VT, AV-block III)

Major bleeding is defined as

- Non-CABG intracranial, intraocular, or retroperitoneal bleeding
- Access-site hemorrhage requiring intervention or resulting in a ≥ 5 cm diameter hematoma
- Reduction in hemoglobin concentration of ≥ 4 g/dL without or ≥ 3 g/dL with an overt bleeding source
- Reoperation for bleeding
- Blood product transfusion

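### The arrhythmia component of MACE counts documented VT and third-degree AV block, but chances of documentation differ by arm after early discharge; the bias favours the experimental arm and is of unknown, possibly small, size

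*Protocol*

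**What the plan says.** **The endpoint.** Section 5.1 ends the list of primary MACE components with "documented life-threatening arrhythmias (VF, VT, AV-block III)) within 30 days Copeptin vs. Control group". Section 11.1, the definition section, repeats the item as "Documented life-threatening arrhythmias (VF, VT, AV-block III" and adds no threshold. Section 5.2.2 includes it in MACE at 30 and 90 days and lists it again on its own, joined with survived arrest: "Documented life-threatening arrhythmias or survived sudden cardiac arrest".

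**Observation in hospital.** Section 8.6 states: "All CPU patients are under constant monitoring and risk assessment". Section 4.1 describes usual handling of suspected ACS as admission with serial biomarker tests and monitoring. Controls (7.5) and Copeptin-positive experimental patients (7.1) get the standard evaluation.

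**Observation after early discharge.** For Copeptin-negative experimental patients, 7.1 says: "In these patients we abstain from further ACS evaluation and instead discharge them into ambulant care". Before they leave there is a final check: "The visit includes a physical examination, an ECG and an assessment for MACE and bleeding events". Afterwards, "Patients are to see a cardiologist within a maximum of 3 days after discharge"; no rhythm recording is specified for that visit. Section 8.7 says of days 30 and 90: "Both follow-ups are telephone visits to assess" survival, MACE and bleeding. Medical records are requested only after death or hospitalization.

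**The protocol's own view.** Section 14.2.3 calls the major outcomes hard data and regards measurement bias as hardly conceivable.

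**The concern.** An arrhythmia enters the endpoint only if someone recorded it. Symptomatic VT or complete block, or an arrest, will usually surface wherever the patient is. A silent episode surfaces only if a monitor or ECG is running. The intervention itself ends that observation early for one part of one arm; a shorter stay is among the secondary hypotheses in section 5. Randomization therefore cannot balance the difference.

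The direction matters. Section 5 sets out to show that MACE within 30 days of admission is no higher with the Copeptin process. Episodes missed in the experimental arm push towards that conclusion. The controls' monitored stay falls inside the 30-day window, so it counts towards the endpoint. For the stand-alone arrhythmia endpoint, where few events are likely, even one or two missed episodes could change the picture.

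**Working it through.** **1. Side by side: who can have a silent VT or AV-block III episode recorded?**

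| Period | Control | Experimental, Copeptin positive | Experimental, Copeptin negative |
|---|---|---|---|
| Admission to the time of early discharge | in-hospital monitoring | same | same, plus an ECG at the final visit |
| From then to the end of the standard work-up | in-hospital monitoring | same | cardiologist visit, no rhythm recording specified |
| Remainder to day 30 (and day 90) | telephone | telephone | telephone |

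The arms differ only in the middle row, and only in the last column.

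**2. Size.** The protocol gives 446 patients per arm (synopsis) and reference MACE rates of 6.4% and 7.8% (14.2.2). It gives no arrhythmia rate, Copeptin-negative share or length of stay, so there is no stated figure to reproduce. All four inputs below are assumptions:

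- *r*: rate of VT/AV-block III episodes if everyone had the standard work-up, 1% to 2%
- *s*: share of those episodes arising in Copeptin-negative patients. This is one third if they are the lower-risk group, as the trial supposes; it equals an assumed negative share of 60% to 75% if risk is the same in both groups
- *m*: share of episodes seen only through monitoring, 50% to 80%
- *d*: share of those falling after the time of early discharge, 50% to 100%

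Spurious difference = *r* × *s* × *m* × *d*; missed events = 446 × that.

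| Assumptions | Product | Points | Events per 446 |
|---|---|---|---|
| Low | 0.01 × 1/3 × 0.5 × 0.5 | 0.08 | 0.4 |
| Lower risk in negatives, other rates high | 0.02 × 1/3 × 0.8 × 0.5 | 0.27 | 1.2 |
| Equal risk, half after discharge | 0.02 × 0.75 × 0.8 × 0.5 | 0.60 | 2.7 |
| Equal risk, 80% after discharge | 0.02 × 0.75 × 0.8 × 0.8 | 0.96 | 4.3 |
| Ceiling: equal risk, all after discharge | 0.02 × 0.75 × 0.8 × 1.0 | 1.20 | 5.4 |

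The ceiling row takes no account of episodes before discharge, which both arms record. A realistic upper limit is about 1 point.

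**3. What that does to a no-increase conclusion (illustration).** The protocol text shows no margin or alpha; the power calculation is in an appendix that is not shown. Assume a 5-point margin, one-sided alpha 0.025 and a normal approximation with unpooled variance. Let the true excess equal the margin and the recorded experimental rate be lowered by *b*:

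P(false conclusion) = Φ(*b*/SE − 1.96), SE = √[p_C(1 − p_C)/446 + p_E(1 − p_E)/446], p_E = p_C + 0.05 − *b*.

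For p_C = 6.4% and *b* = 1 point: p_E = 10.4%, SE = 0.0185, and Φ(0.54 − 1.96) = Φ(−1.42) = 7.8%.

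| *b* (points) | p_C = 6.4% | p_C = 7.8% |
|---|---|---|
| 0 | 2.5% | 2.5% |
| 0.1 | 2.8% | 2.8% |
| 0.25 | 3.4% | 3.3% |
| 0.5 | 4.5% | 4.4% |
| 1.0 | 7.8% | 7.3% |

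The effect is trivial at the low end and material at the high end.

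**The case against.** The case against has real weight.

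- **The qualifier.** A reader might infer that any documented VT or AV block counts. The text says life-threatening arrhythmias, and a short silent VT run need not meet that. This stands as a limit on the claim. But the bracket names VT and AV-block III with no threshold, so two sites can read it differently.
- **Operational detail.** Thresholds may be set in an SAP or endpoint charter that is not shown, and their absence alone would be no finding. What the protocol itself fixes is an endpoint that depends on documentation, unequal chances of documentation, and a statement in 14.2.3 that such bias is hard to imagine.
- **Monitoring only in the CPU.** This is inferred. Section 8.6 does not name rhythm, is not limited to one arm, and nothing is said about wards or intensive care. Monitoring there would widen the gap.
- **Safeguards.** The ECG before discharge and the cardiologist visit will catch some episodes, but neither is continuous. The Endpoints Committee (5.3) can reject a control's episode that was not life-threatening. It cannot find one that was never recorded, and its stated remit covers the primary and the secondary efficacy endpoints, whereas the stand-alone arrhythmia item is listed under safety.
- **Size.** A reader might multiply the Copeptin-negative share by the monitor-only share and conclude that 0.3 to 1.2 points are lost. That assumes equal arrhythmia risk in Copeptin-negative patients, contrary to the trial's hypothesis, and that no episode precedes discharge. The documents support neither assumption.

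**Conclusion.** The concern holds in a limited form. As written, the arrhythmia component leaves room for silent VT or AV-block III to be recorded in patients who stay and missed in Copeptin-negative patients sent home, and the error runs towards the no-increase conclusion. Section 14.2.3 is not correct for this component.

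The documents do not support the stronger reading that MACE as a whole favours early discharge by construction. The gap affects one component, one subgroup and the period between early discharge and the end of the standard work-up.

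The size cannot be derived from the protocol. It may be small: about 0.1 to at most about 1 percentage point (roughly 0.4 to 4 events per 446), with every input assumed. Against the cited 6.4% to 7.8% MACE rates it may matter little for the primary comparison; it matters more for the stand-alone arrhythmia endpoint.

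**What to change.** 1. **Record the route of detection.** Add a CRF field for each VT or AV-block III episode: came to notice through symptoms, haemodynamic compromise or arrest, or only through monitoring.
2. **Define what counts between arms (5.1, 5.2.2, 11.1).** For MACE and the arrhythmia endpoint, count VT and AV-block III only when the episode came to notice through symptoms, haemodynamic compromise or arrest. VF stays as it is. Treatment of a monitor-only finding should not by itself qualify an episode, because a silent episode can be treated only where someone sees it, and the imbalance would return.
3. **Minimum alternative.** Keep the definition and pre-specify a sensitivity analysis of MACE without monitor-only episodes.
4. **Classification and reporting.** Have the Endpoints Committee classify episodes without knowledge of the arm where possible, and report monitor-only episodes descriptively by arm.
5. **Amend 14.2.3** to acknowledge unequal detection of this component.

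The cost is endpoint wording, one CRF field and a line in the analysis; care, visits and monitoring do not change. The downside is slightly fewer counted events and some reliance on reported symptoms in an open trial, which is why arm-blind classification is worth attempting.

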Inclusion Criteria	Admission to the Emergency Department with symptoms consistent with ACS: - Typical chest pain (with or without ECG-changes, but no ST-elevation) suggestive of unstable angina or non-ST-elevated myocardial infarction (NSTEMI) - Troponin negative at admission according to the current clinical practice Patient willing and able to give written informed consent
Exclusion Criteria	Patients with ST-elevation myocardial infarction (STEMI) Continuing chest pain or recurrent episodes of chest pain under therapy High-risk patients with suspected ACS who need to be hospitalized for reasons independent of their initial troponin result Patients who need to be hospitalized for other medical reasons Patients in need of urgent life-saving interventions Patients under 18 years of age Patients with a life expectancy < 6 months Patients with any condition that leads the treating physician to not consider the patient eligible for the trial
Study endpoints	Primary Endpoint: Rate of MACE (all- cause death or survived sudden cardiac arrest, myocardial infarction, re-hospitalisation for acute coronary syndrome, acute unplanned PCI, coronary artery bypass grafting (CABG) and documented life-threatening arrhythmias (VF, VT, AV-block III)) within 30 days Copeptin vs. Control group Secondary endpoints: Efficacy endpoint of rate of Patients in whom coronary angiography is performed Rate of Patients requiring PCI due to their findings in cardiac catheterization. Rate of bleeding events at 30 and 90 days defined as non-CABG intracranial, intraocular, or retroperitoneal bleeding; access-site hemorrhage requiring intervention or resulting in a ≥ 5 cm diameter hematoma; reduction in hemoglobin concentration of ≥ 4 g/dL without or ≥ 3 g/dL with an overt bleeding source; reoperation for bleeding; or blood product transfusion. Further secondary endpoints evaluate efficacy, safety, cost effectiveness and patient satisfaction of the new process including length of stay in the hospital
Safety	All major cardiac adverse events (MACE) as defined in the protocol and bleeding complications as defined in the protocol will be assessed and documented for the duration of the study.

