8.9 Additional 3 hour blood test

Patients can, on an optional basis, agree to an additional, study-related blood draw at 3 hours after their initial admission. This blood sample will be used to further evaluate the kinetics of Copeptin. Additionally, Troponin will be measured to compare the two markers in these samples.

Patients who agree to the blood draw have to give their separate written consent in a special box of the informed consent form (s. attachment).

9 Risk-benefit-assessment

Copeptin negative patients might experience major adverse cardiac events after discharge, which could have been prevented in case of hospital admission, due to unrecognized acute coronary syndrome.

Precaution:

Patients for this trial are very carefully selected. Patients with concomitant diseases or conditions which require a hospitalisation as well as patients with instable angina despite maximal therapy are excluded from participation. Thus, only stable, symptom-free patients will be discharged. We cannot exclude that of these patients, some will be at risk for ACS-related complications. As a precaution, patients will only be discharged after an appointment with one of our co-operating resident cardiologists has been made via the praxis-connect system as explained in section 7.1. Thus, the onward specialist care of these patients is guaranteed. The co-operating cardiologists will be well informed and trained in all trial-matters. All patients will be re-admitted to the Emergency Department upon any suspicion of risk for complications.

Copeptin positive patients might be regarded as high-risk patients and receive more intensive treatment.

Precaution:

Management of all patients will be closely monitored by the principal investigator of each site to assure suitable care and therapy.

Potential advantages for patients in the experimental arm:

Copeptin negative patients bypass further ACS evaluation and are prevented from hospitalization. Patients might be spared an unnecessary hospital admission and antithrombotic and anticoagulant treatment with their related hazards and side-effects. Patients will profit from the personal care by the resident co-operating cardiologist.

All patients will profit from the close and intense monitoring and follow-up by an experienced clinical research team.

Potential advantages for the general public:

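### The bleeding endpoint counts haemoglobin falls, but no post-baseline haemoglobin is scheduled, so during the index stay silent falls are detected mainly in patients kept for evaluation, which favours the copeptin arm on this component

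*Protocol*

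**What the plan says.** Section 5.2.2 lists bleeding among the secondary safety endpoints, and 11.1 repeats the definition under major bleeding. One component is a "reduction in hemoglobin concentration of ≥ 4 g/dL without or ≥ 3 g/dL with an overt bleeding source". The time points are in the synopsis: "Rate of bleeding events at 30 and 90 days".

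On measurement, the table in 8.6 marks routine blood at screening and nowhere else. Its footnote reads "Including Troponin and CK"; haemoglobin is not named. The row "MACE and bleeding event assessment" is marked at discharge, 30 days and 90 days, with no blood test beside it. For copeptin-negative patients in the experimental arm, 7.1 describes the visit before discharge: "The visit includes a physical examination, an ECG and an assessment for MACE and bleeding events". The optional 3-hour sample in 8.9 is for copeptin and troponin. Section 8.7 says of the later contacts: "Both follow-ups are telephone visits to assess" survival, MACE and bleeding. Medical records are requested after a death or a hospitalisation.

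Section 9 names among the possible advantages for copeptin-negative patients that they may avoid "antithrombotic and anticoagulant treatment with their related hazards and side-effects". Section 14.2.3 argues that the major outcomes are hard data and that measurement bias is difficult to conceive of.

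**The concern.** A fall without an overt source gives the patient nothing to report on the telephone. It becomes an event only if haemoglobin is measured again. Because the protocol schedules no second measurement, whether one exists depends on how long and how intensively the patient is cared for, and that is what randomisation changes. Copeptin-negative patients in the experimental arm leave early; control patients, whatever their copeptin level, go through the usual evaluation.

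If the arms differ in who is re-measured, they differ in how many falls are found, even when the true rates are equal. Less bleeding is also a result that readers would expect from less antithrombotic treatment. A lower count in the copeptin arm would therefore look like confirmation, and a true reduction could not be told apart from non-detection. The analysis cannot recover values that were never taken.

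**Working it through.** The plan states no figure on this point that could be reproduced. The check sets the definition against the schedule and then illustrates the size.

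**Step 1: is a second haemoglobin value provided for?**

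| Contact | Source | Haemoglobin specified? |
|---|---|---|
| Screening | 8.6 | Routine blood; haemoglobin not named, presumably included |
| Optional 3-hour sample | 8.9 | No; copeptin and troponin |
| Visit before early discharge | 7.1 | No; examination, ECG, event assessment |
| Cardiologist visit within 3 days | 7.1 | No; no study data collection described |
| Day 30 and day 90 | 8.7 | No; telephone |
| Death or hospitalisation | 8.7 | Only what the records happen to contain |

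No second value is scheduled in either arm.

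**Step 2: who gets an unscheduled one?** Controls (7.5) and copeptin-positive patients in the experimental arm (7.1) stay for standard evaluation, where repeat blood counts are plausible, although the protocol does not promise them. Copeptin-negative patients in the experimental arm forgo that evaluation. For them a second value arises mainly on re-admission. The difference therefore comes from this one subgroup and from the period in which comparable controls are still in hospital.

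**Step 3: illustration of size.** Let *r* be the true rate of haemoglobin-only events, equal in both arms and unrelated to whether a patient is re-measured. Let *f* and *g* be the shares of the experimental and control arms with no second value. With 446 patients per arm (synopsis):

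- detected, experimental arm = 446 × *r* × (1 − *f*)
- detected, control arm = 446 × *r* × (1 − *g*)
- apparent ratio = (1 − *f*) / (1 − *g*)

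The values of *r*, *f* and *g* are assumptions; the protocol gives none of them.

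| *f* | *g* | Apparent ratio |
|---|---|---|
| 0.5 | 0 | 0.5 / 1 = 0.50 |
| 0.7 | 0 | 0.3 / 1 = 0.30 |
| 0.8 | 0 | 0.2 / 1 = 0.20 |
| 0.5 | 0.2 | 0.5 / 0.8 = 0.62 |
| 0.8 | 0.2 | 0.2 / 0.8 = 0.25 |

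For scale, with *r* = 2%, 446 × 0.02 = 8.9 true events per arm. Controls would show 7.1 (*g* = 0.2) to 8.9 (*g* = 0). The copeptin arm would show 1.8 (*f* = 0.8) to 4.5 (*f* = 0.5). The ratio is below 1 whenever *f* exceeds *g*.

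**Step 4: what moves the ratio back towards 1.** If a share *e* of the falls in early-discharged patients is found through re-admission records, the ratio with *g* = 0 becomes 1 − *f*(1 − *e*). For the whole bleeding composite, let *s* be the share of true bleeds that qualify only by a haemoglobin fall, and suppose the other components are seen equally well in both arms. The ratio with *g* = 0 and *e* = 0 is then 1 − *s* × *f*, which is closer to 1 than 1 − *f* for any *s* below 1. The protocol gives neither *e* nor *s*.

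**The case against.** The strongest case on the other side has four parts.

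- **Values can still arise after early discharge.** Re-admission is provided for (7.6, section 9), hospital records are requested (8.7), and a cardiologist sees these patients within days (7.1). This stands. A reader might infer that such bleeds can be found only in patients kept in hospital; the protocol does not support that. It also does not support saying that haemoglobin is scheduled at screening, since the schedule never names it.
- **The asymmetry is limited in time.** After discharge both arms are followed by telephone, so later silent falls are missed in both. This stands as a limit. It does not remove the difference in detection during the index stay.
- **The illustrated ratio says little about the endpoint.** A reader might take 0.3-0.5 as the bias in the bleeding rate. It is not: it covers haemoglobin-only events, rests on assumed shares, treats every control as re-measured and sets the true rates equal. Section 9 makes a true difference plausible.
- **The protocol makes no bleeding claim.** Bleeding is secondary, appears in none of the hypotheses in section 5, and has no test of its own in 14.2. The remark in section 9 concerns possible avoidance of treatment and is not a claim that bleeding will be lower. This limits the consequence. The endpoint is nevertheless listed as a rate to be reported at 30 and 90 days, and a lower rate would invite that reading.

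It can also be said that component tables and sensitivity analyses belong in the SAP, which is not at hand. That is fair for layout. The mismatch, however, lies between a definition and a visit schedule that the protocol itself fixes, and 14.2.3 sets measurement bias aside without an exception for this component.

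**Conclusion.** The point holds for one component of a secondary safety endpoint. Haemoglobin falls count as bleeds, no post-baseline haemoglobin is scheduled, and the intervention shortens the stay that would otherwise supply one. During the index stay, silent falls will be found mainly in controls and copeptin-positive patients, and hardly at all in early-discharged copeptin-negative patients unless they are re-admitted. The problem is weaker for the 3 g/dL criterion, because overt bleeding may itself lead to medical contact. The direction favours the copeptin arm, provided that usual care re-measures a larger share of controls than of the experimental arm. That is likely, but it is an assumption.

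The protocol does not determine the size. The ratio for haemoglobin-only events is 0.3-0.5 if 50-70% of the experimental arm and no control lacks a second value, and 0.20-0.62 over the wider range of 50-80% and 0-20%. The effect on the composite is smaller by an unknown amount. The primary MACE comparison is not touched by this point.

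**What to change.** Keep the bleeding definition in 5.2.2 and 11.1 and make three additions.

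1. State in 5.2.2 and 14.2 that the between-arm bleeding comparison will also be made without events that qualify only by a haemoglobin fall. All other listed components stay in, including the access-site haematoma of at least 5 cm.
2. Report haemoglobin-only events separately by arm, next to the number of patients per arm with any post-baseline haemoglobin value. Say in advance that no conclusion of less bleeding will be drawn from a difference that rests on those events.
3. Amend 14.2.3 so that its statement on measurement bias excepts this component.

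The cost is one extra analysis and one extra table. The restricted comparison will have fewer events and so less precision. No additional blood draw or visit is required.
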